10.4.1 Analysis of Secondary Efficacy Parameters

The key secondary efficacy endpoint is change from baseline of total eye fluorescein staining score as assessed by expanded NEI scale for study eye will be analyzed in a similar manner as performed for primary endpoint. All other secondary endpoints will also be analyzed in a similar manner.

The other secondary efficacy endpoints are ordered as follows: corneal sum fluorescein staining score as assessed by expanded NEI scale, OSDI, Schirmer's test (unanesthetized), and TFBUT.

Key secondary efficacy endpoint will be tested at alpha=0.05 (two-sided) if primary endpoints are both significant at alpha=0.05.

The other secondary efficacy endpoints will be tested in order by fixed sequence method if the key secondary endpoint is significant.

10.5 Analysis of Safety Data

AEs will be coded using the Medical Dictionary for Regulatory Activities dictionary (the most recent version, ver. 24.1 or later). Frequencies, percentages, severity, and relationship to study drug of patients with TEAEs, serious TEAEs, and TEAEs causing premature study withdrawal and study drug discontinuation will be provided by treatment group. An AE is treatment emergent if it occurs or worsens after the first dose of study treatment. Furthermore, frequencies of occurrence will be given of patients with TEAEs by system organ class; by system organ class and preferred term; by system organ class, preferred term, and maximal severity; by system organ class and preferred term for treatment-related TEAEs; and by system organ class, preferred term, and study day of onset. Separate summaries will be additionally performed for ocular and non-ocular AEs.

The safety laboratory data will be summarized by visit and by treatment group, along with changes from the baseline. The values that are below the lower limit or above the upper limit of the reference range will be flagged. Those values or changes in values, which are identified as being clinically significant, will be flagged.

[REDACTED] systemic clinical evaluation, [REDACTED]
[REDACTED]

Further details will be included in a separated statistical analysis plan.

10.6 Analysis of Exploratory Endpoints

Details will be included in a separated statistical analysis plan.

10.7 Demographic/Baseline Information

Summary statistics will be provided by treatment group for demographics (e.g., age, sex, race, ethnicity, eye color groups, and the prior use of [REDACTED]).

The baseline for all efficacy and safety variables will be Visit 2 (Day 1), while the baseline for clinical laboratory measurements and [REDACTED] will be Visit 1 (Screening Visit).

Further details will be included in a separated statistical analysis plan.

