4.2 Exclusion Criteria

Patients are excluded from the study if any of the following criteria are met in either eye:

1. Have any clinically significant ocular condition

[REDACTED]

2. Have any clinically significant eye conditions

[REDACTED]

3. Have a history of [REDACTED]
corneal refractive surgery, and/or any other ocular surgical procedure
within 12 months

[REDACTED]

- 4.

[REDACTED]

[REDACTED]

[REDACTED]

[REDACTED]

9. Have any history of immunodeficiency disorder, human immunodeficiency virus (HIV), positive hepatitis B surface antigen (HBsAg), positive hepatitis C virus (HCV) antibody, or evidence of acute active hepatitis A (anti-hepatitis A virus immunoglobulin isotype M [HAV IgM]), active coronavirus disease 2019 (COVID-19), or a history of organ or bone marrow transplant. Patients with cured hepatitis C or cured COVID-19 will be allowed
10. Have any significant chronic illness that, in the opinion of the Investigator, could interfere with the study parameters, including, but not limited to, severe cardiopulmonary disease, chronic systemic inflammatory or autoimmune

conditions, poorly controlled hypertension, poorly controlled diabetes, autoimmune thyroid diseases, recent history of Bell's Palsy, Parkinson's disease with a significantly decreased blink rate and patients using a continuous positive airway pressure (CPAP) machine at night, and/or have any abnormal lab values considered clinically significant by the Investigator (retesting is allowed once within the Screening Period)

11. History of cancer within the past 5 years (excluding non-melanoma skin cancer)
[REDACTED]

13. Have known hypersensitivity to the investigational product or its components
[REDACTED]

15. Have a known history of alcohol and/or drug abuse within the past 12 months at Visit 1

16. Have any condition or therapy, which, in the opinion of the Investigator, might pose a risk to the patient, make participation in the study not in the best interest of the patient, or limit adherence to the study medications and procedures, such as substance abuse, dementia, plans to move within a year, and/or history of noncompliance with medication or scheduled appointments

17. Special or vulnerable status (e.g., institutionalized, or person related to or an employee of the sponsor or Investigator)

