4.5.2 Rescreening

Patients who fail to satisfy inclusion and exclusion criteria at screening (Visit 1 or Visit 2) may be rescreened 1 additional time at the discretion of the sponsor. Screen failures due to inclusion and/or exclusion criteria that could transiently change and do not compromise the patient's safety as judged by the Investigator can be rescreened once. Patients who were re-screen failures under the previous version of this protocol (Amendment No. 1) can be re-screened one additional time for this amended protocol (Amendment No. 2), only if the eligibility criteria determining the original screen failures have been revised in this amendment (i.e. corneal sum fluorescein staining score and/or Schirmer score). All eligibility assessments will be repeated regardless of the reason for the screen failure(s) and new subject number will be assigned. Rescreening decision must be confirmed by the sponsor's medical monitor.

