4.5.3 Retesting

Clinical labs with clinically significant abnormalities (per the principal Investigator's [PI] assessment) can be retested 1 time if there is a reasonable expectation that abnormality will resolve within the Screening Period (21 days at maximum). Unscheduled visits should be allowed within Screening Period.

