5.1.2 Unscheduled Visits

[figure not shown]
These visits may be performed in order to ensure patient safety. All procedures performed at an unscheduled visit will be recorded in the source documents and on the Unscheduled Visit eCRF pages. Any procedure indicated in the eCRF that is not performed should be indicated as “not done.”

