6.0 CONDUCT OF STUDY

6.1 Study Masking and Randomization

All arms will be double-masked. The run-in drops will be single-masked for patients.

Before the initiation of study run-in at Visit 1, each patient who provides written informed consent will be assigned a subject code. All subject codes will be assigned in strict numerical sequence at a site and no numbers will be skipped or omitted. If a patient is retested on clinical labs, the same subject code will be used (Section 4.5.3). If a patient is rescreened, the patient will be assigned with a new subject code (Section 4.5.2).

Patients who have signed informed consent and subsequently fail to satisfy inclusion and exclusion criteria are defined as screen failures. For all screen failures, the reason(s) for screen failure will be recorded on the patient's source document and eCRF.

Each patient who meets all the inclusion and none of the exclusion criteria at Visit 1 and Visit 2 will be randomized at the end of Visit 2 by using the IWRS.

Subject codes and kit numbers will be assigned automatically to each patient as they are entered into the IWRS. All patients will be randomized into either vehicle or active treatment group at Visit 2 (Day 1) in a 1:1 ratio. [REDACTED]

[REDACTED] The first approximately 240 (120/arm) randomized patients will be assigned into the 52-week Overall Period and the rest of study population (approximately 380 [190/arm] patients) will be assigned into the 12-week Primary Period.

The site staff will dispense the required kit(s). Both the subject codes and the dispensed study drug kit number(s) will be recorded on the patient's source document and eCRF. Patients, sponsor, CRO, and site personnel will be masked to treatment assignment.

After Visit 6 (Day 85), patients who are randomized to enter the 40-week Extension Period will proceed to Visit 7 (Day 169) until Visit 10 (Day 379). Other patients, who are randomized to enter the 12-week Primary Period only, will proceed to Visit 6.5 (Day 99) for post-dose assessments and will complete the study.

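### Section 10.7 takes the laboratory baseline from Visit 1, so for a patient admitted after a passed retest the change from baseline starts, read literally, from the value that would have excluded them

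*Protocol*

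**What the plan says.** Protocol Section 10.7 sets Visit 2 (Day 1) as the baseline for efficacy and safety variables in general, "while the baseline for clinical laboratory measurements and [REDACTED] will be Visit 1 (Screening Visit"). It names a visit and does not say what happens when more than one pre-dose sample exists.

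A second sample is foreseen. Exclusion criterion 10 in Section 4.2 bars patients who "have any abnormal lab values considered clinically significant by the Investigator (retesting is allowed once within the Screening Period"). Section 4.5.3 says that such results "can be retested 1 time if there is a reasonable expectation that abnormality will resolve within the Screening Period (21 days at maximum"), and adds: "Unscheduled visits should be allowed within Screening Period". Section 5.1.2 says where results from such visits go: "All procedures performed at an unscheduled visit will be recorded in the source documents and on the Unscheduled Visit eCRF pages". Under Section 6.1 the patient's record is continuous: "If a patient is retested on clinical labs, the same subject code will be used".

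Rescreening is a different path. Section 4.5.2 states: "All eligibility assessments will be repeated regardless of the reason for the screen failure(s) and new subject number will be assigned".

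Section 10.5 summarizes laboratory data by visit and arm, with change from baseline. It also flags results outside the reference range, and flags values or changes judged clinically significant. Sections 10.5 and 10.7 both leave further detail to the SAP. Only the addendum to that SAP is available here, and none of its nine items concerns the laboratory baseline.

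**The concern.** A patient who is randomized after a passed retest has two pre-dose results: one bad enough to exclude them, and a later acceptable one closer to the first dose. A rule that names Visit 1 selects the first. If the analyte moves back towards its original level on treatment, the change from baseline shows little movement, or an improvement, where the patient has in fact worsened since just before dosing.

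Laboratory measurement is a listed safety endpoint. Table 1 schedules post-dose samples only at Visit 6 and, for 52-week patients, at Visit 9. A 12-week patient therefore contributes one scheduled change value, and it depends entirely on which pre-dose result is called baseline.

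**Working it through.** The plan gives no figure to reproduce here. The check sets the sections side by side and then uses assumed values to show the size.

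**Which value is baseline?**

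1. The laboratory row of Table 1 is marked at Visits 1, 6 and 9 and is blank at Visit 2, so no later scheduled pre-dose sample replaces the Visit 1 result.
2. Section 4.5.3 allows an unscheduled visit for the retest, so the repeat can be dated after Visit 1 and entered on unscheduled-visit pages (Section 5.1.2).
3. Section 6.1 keeps the subject code, so both results sit in one record. A rescreened patient repeats every eligibility assessment under a new number (Section 4.5.2) and does not have this problem.
4. Section 10.7 makes no exception for a retest. Read literally, the Visit 1 result is baseline.

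**Effect on one patient.** Let V be the Visit 1 value, R the retest value and D the Day 85 value, for an analyte that was abnormally high.

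- Change under Section 10.7 as written: D - V
- Change from the last pre-dose value: D - R
- Difference between the two: V - R, positive for a high value that came down
- The sign reverses whenever R < D < V

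Assumed values, in multiples of the upper reference limit: V = 2.5, R = 0.95, D = 2.2.

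- As written: 2.2 - 2.5 = -0.30
- From the retest: 2.2 - 0.95 = +1.25
- Reference-range flag at Day 85: 2.2 > 1, so it is raised under either baseline

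For an abnormally low value the signs are mirrored.

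**Effect on an arm mean.** If a fraction f of an arm entered after such a retest on the same analyte, the arm's mean change is lowered by f x (V - R) = f x 1.55. With 310 patients per arm (Section 10.1):

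| Assumed f | Patients of 310 | Shift in mean change (x upper limit) |
|---|---|---|
| 1% | 3.1 | -0.016 |
| 3% | 9.3 | -0.047 |
| 5% | 15.5 | -0.078 |
| 10% | 31 | -0.155 |

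Over the whole trial, 1% to 3% of 620 is 6 to 19 patients. The documents do not give the retest rate. Because f counts retests on one analyte, retests spread over several analytes would make each shift smaller.

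**The case against.** A reader might infer that the rule hides on-treatment abnormalities. The documents do not support that. Under Section 10.5 every result outside the reference range is flagged without reference to baseline, and summaries by visit show the observed values. The criteria in Section 9.1.1 for reporting an abnormal test as an adverse event are symptoms, further testing or intervention, a dosing change, withdrawal or added treatment, and a serious outcome; none uses change from baseline. No shift table is mentioned, so a missed shift from normal to high cannot be claimed either.

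A reader might also infer that the rule favors K-161. Retesting comes before randomization, so retested patients are expected in both arms alike, and no bias between arms is expected from the rule itself.

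Three further objections carry weight:

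- *The SAP of May 24, 2023 is not available.* It may already define baseline as the last pre-dose value. The addendum's silence does not settle this in either direction.
- *The retest might count as Visit 1.* Visit 1 is a window (Day -21 to -12), and a repeat inside it could be filed there. Visit 1 would then hold two results, and Section 10.7 does not say which one counts. The error becomes an ambiguity but does not disappear.
- *The remedy has its own selection effect.* A retest value becomes baseline only because it came back acceptable. In patients with labile values, regression to the mean may make later results look slightly worse than they are.

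These limit the reach of the point. None gives a reason to prefer the excluding value as baseline.

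**Conclusion.** The point holds in a narrow form. As written, Section 10.7 selects the excluding laboratory value as baseline for a patient admitted after a passed retest. Change from baseline, and any flag based on change, can then understate or reverse a real worsening for that patient.

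The distortion can be large for the individual and is probably small for the arm mean. The size figures rest on assumed values and assumed retest rates. The reading of the rule rests on the protocol text alone, with the SAP unseen. Only retested patients are affected. The efficacy analyses, alpha and sample size are untouched. Severity is minor, but this is more than missing detail: a stated rule gives the less suitable of two values already in hand.

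**What to change.** Replace the laboratory part of Section 10.7 with: *The baseline for clinical laboratory measurements is the last non-missing value before the first dose of double-masked study drug, including a screening retest.* Align the SAP of May 24, 2023 with this wording, or confirm that it already says so and correct the protocol to match.

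Patients without a retest keep their Visit 1 value. The cost is one sentence in each document and a small change to the derivation, which must also read laboratory results from unscheduled visits. No new data are needed. It would help to report how many patients per arm entered after a retest and to list both of their pre-dose values, so that a reader can see the regression to the mean that the new baseline may bring.

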10.8 Interim Analysis

No interim analysis is planned for this study. Planned analyses at Day 85 including the primary analyses will be performed by unmasked team not involved in the conduct of the study once all patient data until Day 85 are obtained in a fashion to protect the masking of the patients who will be followed in extension. Masked team will have access only to a summary of the results comparing the two arms so the same study team can continue to be masked while conducting the remaining part of the trial until the end of the 52-week Overall Period. The investigational sites will not be unmasked and will not have access to the summary of the results comparing the two arms.

10.9 Pharmacokinetic/Pharmacodynamic Analysis

Not applicable.

11.0 STUDY MANAGEMENT AND DATA COLLECTION

11.1 Ethical Conduct of the Trial

The study will be performed in accordance with the ethical principles that have their origin in the Declaration of Helsinki, the HIPAA, and the ICH harmonised tripartite guideline E6(R2): GCP. The study will also be performed in compliance with the requirements of the US FDA as outlined in Title 21 of the CFR (Parts 11, 50, 54, 56, and 312) and all other applicable regional or local regulatory requirements.

11.2 IRB/IEC/REC

The IRB/IEC/REC must be assembled according to the applicable state and federal requirements of each participating location, including ICH E6(R2) guidelines, and US FDA 21 CFR Part 56.

It is the responsibility of the clinical site to submit the Protocol, Investigator's Brochure, patient ICF, patient recruitment materials (if applicable), and other documentation as required by the IRB/IEC/REC for review and approval. A copy of the written approval must be provided to KRI. The documentation must clearly mention the approval/favorable opinion of the Protocol, the patient ICF, and patient recruitment materials (if applicable), including respective version dates. The written approval and a list of the voting members, their titles or occupations, and their institutional affiliations must be obtained from the IRB/IEC/REC and provided to KRI before the release of clinical study supplies to the clinical site and commencement of the study. If any member of the IRB/IEC/REC has direct participation in the study, written notification regarding his or her abstinence from voting must also be obtained.

The clinical site must adhere to all requirements stipulated by the IRB/IEC/REC. This includes notification to the IRB/IEC/REC regarding the following: protocol amendments, updates to the patient ICF, recruitment materials intended for viewing by patients, IND safety reports, serious and unexpected AEs, reports and updates regarding the ongoing review of the study at intervals specified by the IRB/IEC/REC, and submission of final study reports and summaries to the IRB/IEC/REC.

It is the responsibility of each investigational site to submit information to the appropriate IRB/IEC/REC for annual review and annual re-approval.

11.3 Patient Informed Consent

Written consent must be obtained from the patient prior to any study-specific procedure or investigation.

Prior to the implementation of study procedures, patients and persons conducting the consent discussion will be required to sign and date the IRB/IEC-approved ICF, and each patient will be given a copy. In addition, this information will be recorded in the patient's medical record (i.e., source document).

The written consent document will embody the elements of informed consent as described in the HIPAA, World Medical Association Declaration of Helsinki, FDA 21 CFR Part 50.25, ICH GCP, and in accordance with any local regulations. The Investigator is responsible for the preparation, content, and IRB/IEC/REC approval of the ICF. The ICF must be approved by the clinical site-designated IRB/IEC/REC and be acceptable to KRI or its designee prior to their use.

The ICF must be written in a language fully comprehensible to the prospective patient. The written patient ICF will explain the objectives of the study and its potential risks and benefits. The information included on the ICF must be provided to the patient both verbally and in writing whenever possible and in a manner deemed appropriate by the IRB/IEC/REC. Patients must be given ample opportunity to read the information and inquire about details of the study. The Investigator must be satisfied that the patient has understood the information provided before written consent is obtained. If there is any doubt as to whether the patient has understood the written and verbal information, the patient must not be allowed to enter the study.

If a patient agrees to participate, he or she will be asked to sign and date an ICF, the original copy of which will be kept by the Investigator. A copy of the signed ICF will be given to the patient. Information documenting the informed consent procedure will be recorded in the patient's medical records (i.e., source document), and the original signed ICF must be made available to the study monitor for inspection.

If informed consent is taken under special circumstances (oral informed consent), then the procedures to be followed must be determined by CRO and/or the sponsor and provided in writing by CRO and/or the sponsor prior to the consent process.

All ICFs must be approved for use by the sponsor or designee and receive approval/favorable opinion from an IRB/IEC/REC prior to their use. If the ICF requires revision (e.g., due to a protocol amendment or significant new safety information), it is the PI's responsibility to ensure that the amended form is reviewed and approved by the sponsor prior to submission to the governing IRB/IEC/REC and that it is read, signed, and dated by all patients or their designees currently and subsequently enrolled in the study.

11.4 Amendments to the Protocol

An amendment must be agreed to in writing by the sponsor, submitted to FDA as an IND application amendment, and submitted to and approved by the respective IRB/IEC/REC for each investigational site before it is implemented. Written approval of a protocol amendment is not required prior to implementation for changes to the protocol, which eliminate immediate hazard to the patient; however, approval must be obtained as soon as possible thereafter. Approved amendments must also be signed by the Investigator.

11.5 Study Initiation

The Investigator must not enroll any patients prior to the completion of a formal meeting conducted by a representative of the sponsor. This meeting will include a detailed review of the study protocol and eCRFs. Study drug will not be supplied to an Investigator until

all the necessary pre-study requirements have been completed and essential signed documents are received by the sponsor or its representative.

11.6 Study Monitoring

It is the responsibility of the Investigator to ensure that the study is conducted in accordance with the protocol, ICH/FDA GCPs, applicable regulatory requirements, HIPAA, and the current Declaration of Helsinki. Valid data are to be entered into the eCRFs.

To achieve this objective, the monitor's duties are to aid the Investigator and, at the same time, the sponsor in the maintenance of accurate, complete, legible, well-organized, and easily retrievable data. The monitor will review the protocol with the Investigator. In addition, the monitor will explain the Investigator's reporting responsibilities and all applicable regulations concerning the clinical evaluation of the study drug.

The Investigator will permit the representatives of the sponsor to monitor the study as frequently as the sponsor deems necessary to determine that data recording and protocol adherence are acceptable. The eCRFs and related source documents will be reviewed in detail by the monitor at each visit, in accordance with relevant standard operating procedures, ICH GCP guidance, and FDA GCP regulations. This includes results of tests performed as a requirement for participation in this study and any other medical records required to confirm information contained in the eCRFs, such as past medical history and secondary diagnoses. The Investigator and staff will be expected to cooperate with the monitor and provide any missing information, whenever possible.

All monitoring activities will be reported and archived. In addition, monitoring visits will be documented at the investigational site by signature and date on the study-specific monitoring log.

